Statistical Analysis Plan

Effects of mobilization dose in surgical intensive care unit patients on adverse discharge disposition

Original Date: August, 20, 2018

Table of Contents

1. Primary and Secondary Aim Overview.....	2
2. Primary aim.....	2
Hypotheses.....	2
Covariate Data.....	3
Statistical analysis.....	3
3. Secondary aim.....	5
Hypothesis.....	5
Statistical Analysis.....	5
4. Sample Size.....	6
5. Data collection.....	6

1. Primary and Secondary Aim Overview

Primary Aim

The primary aim of this study is to assess the effects of mobilization dose in critically ill patients on adverse discharge disposition (ADD) (primary outcome). The primary hypothesis of this study is that the mobilization dose in the surgical intensive care unit measured by Mobilization Quantification Score (MQS) is associated with ADD.

Secondary Aim

The secondary aim is to evaluate the association between rectus femoris cross sectional area (RFCSA) measured by bedside ultrasound within 48 hours of enrollment and mobilization dose received in the surgical intensive care unit (SICU).

2. Primary Aim

This study aim is driven by the research hypothesis that the MQS - a new method to quantify mobilization dose based on intensity and duration with more granularity than currently used mobilization quantification instruments - reflects the improving effects of early mobilization on discharge disposition.

Exposure variable

The primary exposure variable is the mean daily mobilization dose quantified by the MQS. The MQS is a newly developed score that quantifies mobilization provided by SICU nurses and physical therapists incorporating the mobilization level as well as its duration. The MQS is calculated daily throughout the SICU stay and will be divided by the number of ICU days to arrive at the exposure variable mean daily mobilization dose.

The secondary exposure variable used for comparison is the SICU optimal mobilization score (SOMS).

Primary Outcome

The primary outcome ADD is defined as discharge to facilities providing long-term care assistance for daily activities, including nursing homes and skilled nursing facilities, hospice at the patient's home, hospice in a healthcare facility, or in-hospital mortality.

Hypotheses

Primary Hypothesis

The primary hypothesis is that mobilization dose quantified via MQS predicts adverse discharge disposition.

Secondary Hypothesis

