The key secondary hypothesis is that the MQS predicts ADD better than the SICU optimal mobilization score [SOMS] (Schaller et al., 2016).

We also hypothesize that the MQS predicts ICU length of stay, hospital length of stay, functional independence measure (mmFIM) at ICU and hospital discharge, 3-month mortality, change in muscle mass quantified by change in RF-CSA, ICU coma- and delirium-free days, ICU ventilator-free days, ICU vasopressor-free days, ICU neuromuscular blocking agent free days, opioid dosage, corticosteroid days, and physical work capacity 3 months after hospital discharge quantified by the Duke Activity Status Index (DASI).

Covariate Data

Predefined confounders in multivariable adjusted analyses include APACHE2 (Knaus, Draper, Wagner, & Zimmerman, 1985), sex-adjusted rectus femoris cross sectional area (RFCSA) (Janssen, Heymsfield, Wang, & Ross, 2000) measured via bedside ultrasound upon admission, and the Risk Quantification Index for 30-day Postoperative Morbidity (PSS morbidity) (Dalton et al., 2011).

RFCSA measured by bedside ultrasound has been shown to be an independent predictor of adverse patient outcomes (Mueller, Eikermann 2016).

RFCSA will be adjusted for sex using published skeletal muscle mass values of the lower body of healthy adults (Janssen et al., 2000). Thus, RFCSA of female patients are multiplied with the coefficient 1.484, whereas male patients represent the reference group (adjustment coefficient 1). Sex-adjusted RFCSA will be used for further statistical analyses.

Statistical Analysis

All analyses are performed prospectively with prespecified endpoints and statistical methods.

Primary analysis

Unadjusted Analysis: We will conduct univariate logistic regression analysis to investigate the association between mobilization dose quantified by MQS and ADD.

Adjusted analysis: Multivariable logistic regression (mean daily mobilization dose (MQS)/ ADD) analyzing whether mobilization dose predicts adverse discharge independent from the defined covariates (APACHE2, PSS Morbidity score, and sex adjusted admission RFCSA).

Secondary analyses

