We will perform Net Reclassification Index and c-statistics to compare the predictive capability for ADD of the MQS to the SOMS. To further confirm the robustness of our results we will conduct Aikaike Information Criterion (AIC) and likelihood ratio test. AIC provides the relative quality of the estimated model. The likelihood ratio test compares the goodness of fit of two statistical models.

Multivariable logistic regression will be performed to evaluate the relationship between mean daily mobilization dose and other binary secondary outcomes controlling for above defined covariates. Zero truncated negative binomial regression will be used to analyze the association between mobilization dose and the secondary outcomes ICU and hospital length of stay. Negative binomial regression will be used to analyze the association between mobilization and the secondary outcomes coma- and delirium-free days, NMBA-free days, ventilator-free days, and functional independence measure (mmFIM) at ICU and Hospital discharge.

We will use linear regression to analyze the association between mobilization and physical work capacity 3 months after hospital discharge quantified by the Duke Activity Status Index (DASI) and opioids dosage (mg), if normality assumption is satisfied. Otherwise, transformation of the variables will be performed, and the transformed variables will be used as the outcome in the linear model.

Planned Sensitivity Analyses

Evaluation of confounder model: AUC-Analysis including the predefined confounders to determine the Area Under the receiver operator curve.

Categorized exposure variable: (2-quantile [high, low mobilization dose], tertiles [low, intermediate, high mobilization dose])

Alternative Exposure Variable: For each patient, mobilization data will be centered, and we will perform simple linear regression with the individual mean mobilization dose being the estimated intercept of each patient. The estimated slope from the linear regression will be considered as the change rate of mobilization dose. Two exposures will be included in our model, the slope of the mobilization dose and the intercept. We will conduct multivariable logistic analysis controlling for the same confounder variables (expected 4DoF: Intercept, Slope, APACHE2, RFCSA (continuous), PSS morbidity) from the primary analysis.

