Evaluate the AUC with alternative Exposure Variable (intercept/ slope): We will compare discriminative ability of our primary model to a model with two exposure variables (intercept (mean mobilization dose for each patient) and slope) utilizing Net Reclassification Index, Brier Score and c-statistics.

Generalized propensity score: In an exploratory approach, accounting for the degrees of freedom available, we will include a generalized propensity score to reduce bias induced by discrepancies in patient characteristics. The propensity score will be generated from different covariates identified as influencing the exposure including APACHE, GCS at enrollment, ASA at admission, PSS-Morbidity, duration of ventilation, duration of sedation, duration of delirium, opioid dose, vasopressors. The propensity score will be confined for a binary exposure variable. To derive at a binary variable, we will categorize the mean mobilization dose (MQS) into two categories, high vs. low.

Subgroup analyses: We will perform a subgroup analysis in patients who received surgery upon admission to the ICU.

Planned Exploratory Analyses

We aim to explore the association of other variables that can be used to quantify mobilization intensity and duration (other than the composite exposure MQS) and adverse discharge disposition.

The additional variables used to quantify mobilization intensity and/or dose are:

- Mean highest achieved level of mobilization therapy (Daily highest achieved ICU mobilization scale level/ICU days)
- Highest achieved mobilization level using ICU mobilization score
- Mean number of daily mobilization sessions (Total number of mobilization units/ICU days)
- Mean duration of mobilization units according to MQS (Total duration of mobilization treatment based on MQS/number of sessions throughout the ICU stay)
- Fraction of days mobilized (Number of mobilization days/ ICU days)
- Early mobilization frequency (Total number of mobilization units from day 1 through 3 on the ICU)

We will use multivariable logistic regression for exploratory analyses analyzing the association between the above-mentioned variables used to quantify mobilization intensity and/or dose.

3. Secondary Aim

Exposure variable

The RFCSA assessed through bedside ultrasound measurements within 48h is used as a continuous exposure variable.

Outcomes

The outcome for the secondary aim of the study is the repeatedly measured daily mobilization dose as quantified by the MQS.

Hypothesis

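### The exploratory propensity score adjusts for in-stay durations, and for opioid dose and vasopressors with no time window, that mobilization may itself change; a null or harmful result would be ambiguous

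*SAP*

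**What the plan says.** Under Planned Sensitivity Analyses, the SAP describes an exploratory propensity score meant "to reduce bias induced by discrepancies in patient characteristics". Its inputs are "covariates identified as influencing the exposure including APACHE, GCS at enrollment, ASA at admission", PSS-Morbidity, and then "duration of ventilation, duration of sedation, duration of delirium, opioid dose, vasopressors". GCS and ASA carry a time point. The last five carry none.

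The exposure is a whole-stay mean (Exposure variable, primary aim): "The MQS is calculated daily throughout the SICU stay and will be divided by the number of ICU days". For the score it is cut into high and low.

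Under Secondary Hypothesis, the SAP expects MQS to predict, among others, "ICU coma- and delirium-free days, ICU ventilator-free days, ICU vasopressor-free days, ICU neuromuscular blocking agent free days, opioid dosage". Under Secondary analyses it fits "the association between mobilization and the secondary outcomes coma- and delirium-free days, NMBA-free days, ventilator-free days" by negative binomial regression, and opioid dose by linear regression alongside the three-month activity score ("Duke Activity Status Index (DASI) and opioids dosage (mg), if normality assumption is satisfied").

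The aim is stated as being to "assess the effects of mobilization dose in critically ill patients on adverse discharge disposition".

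**The concern.** A propensity score removes confounding when its covariates are settled before the exposure acts. A duration of ventilation, sedation or delirium is known only when the condition ends, which is during or after the period over which MQS is averaged. If mobilization shortens these durations, adjusting for them removes part of the effect under study. If an unmeasured factor also drives both the duration and adverse discharge (ADD), the adjustment can create an association in the harmful direction.

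The SAP calls these variables influences on the exposure in one place and lists most of them as things the exposure predicts in another. What is at stake is the reading of the sensitivity analysis: a null or harmful estimate would be set against the primary result although it might reflect only the choice of covariates.

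**Working it through.** **Step 1: set the passages side by side.**

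| Score covariate | Window stated? | Counterpart among the quantities MQS is hypothesized to predict |
|---|---|---|
| Duration of ventilation | No; accrues in stay | Ventilator-free days (complement) |
| Duration of sedation | No; accrues in stay | None listed |
| Duration of delirium | No; accrues in stay | Coma- and delirium-free days (complement) |
| Opioid dose | No; could be baseline or stay total | Opioid dosage (direct) |
| Vasopressors | No; could be baseline or stay total | Vasopressor-free days (complement) |

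Four of five overlap: three by complement, one directly. Secondary analyses names a model for three of the four; vasopressor-free days is not named there.

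**Step 2: the plan's own figures.** The SAP gives no number for this analysis. Its only related figure is a power above 0.8 at N = 150 and correlation 0.25. It reproduces (two-sided, Fisher z): Φ(atanh(0.25) × √147 − 1.96) = Φ(3.097 − 1.960) = 0.872. This point does not touch it.

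**Step 3: large-sample illustration (200,000 patients, all coefficients assumed).** S is baseline severity, U an unmeasured cause, and each equation has standard normal noise.
- Early burden M0 = 0.6S + noise.
- Dose = −0.5S − 0.5·M0 + noise, cut at its median to give H (high = 1).
- Whole-stay burden M = M0 − bH + uU.
- Log odds of ADD = −0.5 + 0.5S + 0.6M + 0.6uU + dH.

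Risk differences for high versus low dose, stratified on a score built from:

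| Case | Truth | S only | S + early burden | S + whole-stay burden |
|---|---|---|---|---|
| Benefit only through burden (b = 0.8, u = 0, d = 0) | −0.090 | −0.184 | −0.096 | −0.005 |
| Same, with unmeasured cause (u = 1) | −0.078 | −0.152 | −0.078 | +0.076 |
| Direct benefit added to the first case (d = −0.4) | −0.157 | −0.241 | −0.158 | −0.075 |
| No effect (b = 0, u = 0, d = 0) | 0.000 | −0.093 | −0.002 | −0.002 |

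With whole-stay burden, the first and last rows give nearly the same answer. The early-burden score does well by construction, because early burden is the only other confounder here. Leaving burden out altogether is also biased.

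**Step 4: trial-size illustration (n = 150, median split, 1,000 to 2,000 runs per cell, all coefficients assumed).** One duration stands in for the five covariates. The logit of the score enters a logistic ADD model; the SAP does not say how its score is to be used.

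*Real effect, log OR −1 (e^−1 = 0.37), part of it through a duration that high dose shortens by 1 SD:*

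| Share through duration | 0% | 25% | 50% | 75% | 100% |
|---|---|---|---|---|---|
| Median OR, duration in score | 0.37 | 0.48 | 0.59 | 0.78 | 0.99 |
| Significantly protective | 72% | 45% | 26% | 9% | 3% |
| Median OR, enrollment-day score | 0.36 | 0.37 | 0.37 | 0.40 | 0.43 |

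*No effect on ADD, dose shortens duration, unmeasured cause of duration and ADD (8 cells):* with duration in the score, OR 1.09 to 1.59, significantly harmful in 4.5% to 22% of runs; enrollment-day score 0.99 to 1.01.

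*No effect, duration lowers dose and raises ADD (18 cells):* with duration, OR 0.99 to 1.03, falsely protective in 1.7% to 2.9% (nominal 2.5%); enrollment-day score 0.93 down to 0.52, falsely protective in 3.5% to 46%.

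*Both paths at once (24 cells):* a reference score using severity and the true underlying need gave 0.36 to 0.42. The score with duration gave 0.46 to 1.04 and the enrollment-day score 0.25 to 0.38. The reference lay between the two in every cell.

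*No effect, one unmeasured cause lowers dose, lengthens duration and raises ADD (24 cells, 1,500 runs each):* the in-stay score was falsely protective in 0.3% to 31% of runs, and both scores together in 0.3% to 22%. In one cell (dose slope −0.5, duration 0.5, ADD log odds 1, no shortening) the ORs were 0.64 (enrollment-day) and 0.59 (in-stay), both significant in 22% of runs.

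**The case against.** The best defence is that these variables are real confounders. Ventilated, sedated or delirious patients may be mobilized less because of their state, which is the SAP's stated reason for including them. Where duration drives dose and there is no effect, the SAP's version kept its error rate and the enrollment-day version did not. This stands, and it is why the in-stay score should be kept.

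Other points also stand. The hypotheses speak of prediction and association, and prediction does not make a variable a mediator; only the aim speaks of effects. Opioid dose and vasopressors could be baseline values, since Data collection records both. The covariate list is open-ended and subject to the available degrees of freedom.

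Three stronger readings are tempting, and the document supports none of them:
- *That all five covariates are certainly post-exposure.* This is firm for the three durations and conditional for the other two.
- *That the in-stay variables should be replaced by enrollment-day ones.* That exchanges one bias for another. The SAP also does not say that enrollment precedes the first mobilization, so enrollment-day values may not be strictly pre-exposure.
- *That a protective result in both versions would confirm the primary finding.* An unmeasured cause of dose, duration and ADD can make both falsely protective, as the last set of simulations shows.

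**Conclusion.** The point holds and is minor. As written, the score may condition on consequences of mobilization, so it does not estimate the total effect, and a null or harmful result could mean no effect, a mediated benefit or an induced association. This is more than an unstated detail, because the SAP gives four of the five variables both roles.

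A reader might infer that the trial's main conclusion is compromised. It is not: the primary adjusted model uses APACHE2, PSS morbidity and admission muscle area only, and the score is labelled exploratory.

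The textual finding rests on the SAP alone. Every simulation coefficient is assumed, so the figures show direction and ambiguity; the size of any bias in this trial is unknown. Calling a score confined to a binary exposure generalized is a clerical matter.

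**What to change.** State the time window for each of the five covariates, fit the score twice, and report both without ranking them.

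- **(a) Enrollment-day, or earliest recorded, values:** APACHE II, GCS, ASA, PSS-Morbidity, and ventilation, sedation, opioid and vasopressor status, plus delirium if a CAM-ICU result exists for that day. Note that this version may leave in-stay confounding and that the first mobilization may precede enrollment.
- **(b) In-stay durations and doses:** labelled as conditioning on variables that accrue during the exposure.

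Prespecify three cautions and no decision rule:
1. Disagreement between (a) and (b) cannot separate mediation from in-stay confounding.
2. An odds ratio near or above 1 in (b) alone is not evidence of no effect or of harm.
3. Agreement on a protective result does not exclude unmeasured confounding.

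Rename the score to match its binary exposure.

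The cost is SAP wording and one extra fit. Version (a) has at most nine covariates (4 + 5), the number listed now. The data are largely in hand: Data collection has medication and ventilation noted daily, and intubation and extubation dates are listed under Ventilation/ABG. CAM-ICU is listed without a stated frequency, hence the condition on delirium. The downside is a possibly less clear-cut sensitivity result.

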Primary hypothesis

The primary hypothesis is that RFCSA is an independent predictor of mobilization dose in the SICU.

Statistical Analysis

All analyses are performed prospectively with prespecified endpoints and statistical methods.

We will conduct a generalized linear mixed effect model to analyze whether the RFCSA quantified via bedside ultrasound is an independent predictor of daily mobilization dose in the ICU.

Predefined confounders include the Barthel Index at hospital admission, APACHE2 and Charlson Comorbidity Index (CCI).

Secondary analysis

We will conduct a generalized linear mixed effect model to analyze whether the RFCSA quantified via bedside ultrasound is an independent predictor of daily mobilization dose in the ICU utilizing an alternative exposure variable. The exposure variable will be the binary variable "Sarcopenia

yes/no". Sarcopenia is quantified by RFCSA assessed through bedside ultrasound measurements within 48h. We will apply Youden's Index to define the optimal cutoff point of RFCSA for Sarcopenia. (Mueller, Eikermann 2016).

Sarcopenia is a clinical syndrome that describes progressive and generalized loss of skeletal muscle mass and strength and is associated with patient outcomes. (Delmonico, Harris, Lee, J Am Geriatr Soc, 2007)

Sample Size and Power

Based on data obtained by the same centers in the SOMS trial (Schaller et al., 2016) there is a correlation between mobilization dose and discharge disposition of 0.25. We therefore calculate that a sample size of 150 patients provides a power of >0.8 to identify a significant effect (alpha-error: 0.05) for our primary outcome.

Data collection

Data collection

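### The exploratory exposure for early mobilization is a raw total over ICU days 1 to 3, so it mixes daily frequency with days present in the ICU

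*SAP*

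**What the plan says.** Planned Exploratory Analyses lists six alternative ways to quantify mobilization, each to be related to ADD. The last is "Early mobilization frequency (Total number of mobilization units from day 1 through 3 on the ICU". Its neighbours carry a per-day denominator: "Mean number of daily mobilization sessions (Total number of mobilization units/ICU days", "Fraction of days mobilized (Number of mobilization days/ ICU days" and "Mean highest achieved level of mobilization therapy (Daily highest achieved ICU mobilization scale level/ICU days". Mean duration is divided by the number of sessions. The one other item without a denominator, the highest level achieved, is a maximum and not a count. The primary exposure is also normalized: the MQS "will be divided by the number of ICU days to arrive at the exposure variable mean daily mobilization dose" (Primary Aim, Exposure variable).

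The outcome includes "hospice at the patient's home, hospice in a healthcare facility, or in-hospital mortality" (Primary Outcome). For the model, the SAP says "We will use multivariable logistic regression for exploratory analyses". It gives no rule for patients whose ICU stay ends before the end of day 3 and states no minimum stay. Eligibility may be settled in the protocol, which is not at hand.

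**The concern.** A count over a fixed three-day window measures frequency only if every patient is present for the whole window. Otherwise it is the product of two things, how often the patient was mobilized per day and how many of the three days the patient spent in the ICU.

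The second factor is related to the outcome. A patient who dies on ICU day 1 or 2 has a truncated count and is an ADD event by definition, and the same holds for an early move to hospice. A well patient transferred early also has a truncated count but is less likely to go on to ADD. Ill early leavers make a low count look harmful, so early mobilization appears protective. Well early leavers do the reverse.

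This is the only listed exposure confined to the early ICU period, so it is the one a reader would cite on early mobilization.

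**Working it through.** **Plan's own figure.** The SAP gives no figure for this exposure. Its one design figure is the power for the primary outcome, based on the statement that "there is a correlation between mobilization dose and discharge disposition of 0.25", with 150 patients and alpha 0.05. By Fisher's z, two-sided: atanh(0.25) × √(150 − 3) − 1.960 = 0.2554 × 12.124 − 1.960 = 1.137, and Φ(1.137) = 0.87. The stated power of more than 0.8 is reproduced, and nothing below depends on it.

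**Step 1: arithmetic of the definition.** Let r be units per day and d the days present within days 1 to 3. The expected score is T = r × d, and the per-day version is T/d = r.

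| Daily rate r | T, 1 day | T, 2 days | T, 3 days | T/d |
|---|---|---|---|---|
| 1 | 1 | 2 | 3 | 1 |
| 2 | 2 | 4 | 6 | 2 |
| 3 | 3 | 6 | 9 | 3 |

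At equal r, a stay of one or two days yields 1/3 or 2/3 of the three-day score. Ranks can reverse: 2 units on a single day score 2, while 1 unit per day for three days scores 3, although the first patient was mobilized twice as often per day. With d = 3 for everyone, T is exactly 3r and there is no distortion.

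**Step 2: direction of bias.** All inputs here are assumptions: session counts gamma-Poisson with mean 1.5 per day; early leavers present 1 or 2 days with equal probability; ADD 50% in patients present all three days; daily rate unrelated to leaving or to outcome, so the true odds ratio is 1.00. With 400,000 simulated patients per row and unadjusted logistic regression:

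| Early leavers | ADD among leavers | OR per unit, raw total | OR per unit, per-day |
|---|---|---|---|
| 0% | n/a | 0.999 | 0.996 |
| 10% | 0% | 1.042 | 0.994 |
| 10% | 50% | 1.001 | 1.005 |
| 10% | 100% | 0.959 | 1.003 |
| 20% | 0% | 1.085 | 1.001 |
| 20% | 50% | 1.000 | 1.001 |
| 20% | 100% | 0.921 | 0.993 |

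The raw total moves away from 1 in the direction set by the leavers' risk. It does not move when leavers carry the same risk as everyone else.

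**Step 3: false positives at the trial's size.** Assumptions: n = 150, mean 1.5 units per day, ADD 40% in patients present all three days, 15% in well leavers, 80% in ill leavers; rate unrelated to leaving; no true effect; unadjusted model; 5% level.

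| Early leavers | Raw total rejects | Per-day version rejects |
|---|---|---|
| 10-30%, all well | about 6-13% | 3-7% |
| 10-30%, all ill | about 10-25% | 3-7% |
| 10-30%, mixed | about 4-5% | about 4-5% |
| 5% | about 4-5% | about 4-5% |

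The upper ends depend on how widely session rates are assumed to vary between patients. Other runs of this kind put them at 12-16% for well leavers and 24-32% for ill leavers.

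**The case against.** The strongest case against acting has five parts.

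- **Eligibility is not visible.** A minimum ICU stay in the protocol would remove the problem, and the SAP gives no distribution of stay. This stands: the size is conditional, and the 10-30% of early leavers is an assumption.
- **Opposite leavers cancel.** With well and ill leavers mixed, the false-positive rate stays near 5%. This also stands, but the SAP gives no reason to expect such a balance.
- **The model simulated is not the one planned.** The SAP plans multivariable regression, and the confounders named under Covariate Data (APACHE2, PSS morbidity, sex-adjusted RFCSA) may absorb part of the bias if they are used here. That is fair. None of them is days present, however, so the mechanical link is not removed directly.
- **The per-day version can be confounded too.** If well leavers are mobilized 1.5 times as often and ill leavers less, a simulation at 20-30% leavers gave the per-day version an OR of 0.89-0.94 and a rejection rate of 6-13%. In one scenario (30% leavers, 60% of them well) it rejected more often than the raw total, 12% against 7.5%. This is true, but it is confounding by health, which affects every exposure in this SAP. It is no argument for adding a second dependence on length of stay.
- **A per-day session measure is already listed.** For stays of three days or fewer it equals the proposed version. For longer stays it does not isolate the early period, which is the purpose of this item.

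A reader might also infer that early leavers are scored as low-dose whatever their true daily frequency. The definition does not support that. The total still rises with rate: 3 units per day for two days gives 6, against 3 for 1 unit per day over three days. In the simulation of step 2, about 64-78% of early leavers fell below the overall median, against 29-44% of patients with full stays, so 22-36% of leavers did not.

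**Conclusion.** The point holds in limited form. As defined, the measure understates daily frequency for anyone not in the ICU on all three days, relative to a patient with the same daily frequency who is. Because days present are linked to ADD, its association with ADD can be biased either way.

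The size cannot be fixed from the SAP. It ranges from no bias if all patients stay at least three days, through negligible with few or mixed leavers, to the inflated error rates in step 3 if leavers are predominantly well or predominantly ill. Those rates rest on assumed leaver shares and risks, a session rate unrelated to leaving, and an unadjusted model.

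It would be wrong to read this as a threat to the trial's main conclusions. The measure is one of six exploratory exposures, and the primary analysis, the key secondary comparison with the SOMS and the sample size do not use it. Severity is low: a cheap, optional improvement.

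**What to change.** Redefine the item as the number of mobilization units on ICU days 1 to 3 divided by the number of those days the patient was in the ICU, counting days as for the other per-day measures.

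The cost is one line of SAP text. No new data are needed, since ICU admission and ICU discharge dates are already listed under Data collection. If every patient stays three days, the variable is only rescaled by 1/3. The downside is a noisier value for patients present one or two days. The change removes the mechanical dependence on days present. It does not remove confounding by illness severity, which still has to be handled by covariate adjustment.
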